1 PROTOCOL SUMMARY

A study to confirm the safety and effectiveness of the BSJ003W in Japanese patients with non-valvular atrial fibrillation at increased risk of thromboembolism in Japanese clinical environment	
Study Objective(s)	To confirm the safety and effectiveness of the BSJ003W in Japanese patients with non-valvular atrial fibrillation at increased risk of thromboembolism in Japanese Clinical environment
Planned Indication(s) for Use	To reduce the risk of thromboembolism from the Left Atrial Appendage in patients with non-valvular atrial fibrillation who are at increased risk based on CHADS ₂ or CHA ₂ DS ₂ -VASc scores
Test Device	BSJ003W LAA Closure Technology; three-component system consisting of the 
 • BSJ003W Closure Device; WATCHMAN(Gen 2.5) • BSJ003W Delivery System (Delivery Catheter and BSJ003W Closure Device) • BSJ003W Access System (Access Sheath and Dilator)
Control Device	None
Device Sizes	21mm, 24mm, 27mm, 30mm, 33mm
Study Design	This is a prospective, multi-center, single-arm study to confirm the safety and effectiveness of BSJ003W for Japanese subjects with non-valvular atrial fibrillation who are eligible for long-term anti-coagulation therapy to reduce the risk of stroke but who have a rationale to seek a non-pharmacologic alternative in Japanese clinical environment.
Planned Number of Subjects	One Roll-in subject per site is required prior to enroll an analyzable subject at each site. One more Roll-in subject should be enrolled if necessary per Investigators' or a proctor's discretion. Number of analyzable patients: 40 patients. Maximum of 60 subjects (including 10-20 Roll-in subjects) will be enrolled in the study.
Planned Number of Investigational Sites	Up to 10 investigational centers in Japan

A study to confirm the safety and effectiveness of the BSJ003W in Japanese patients with non-valvular atrial fibrillation at increased risk of thromboembolism in Japanese clinical environment

Primary Endpoints

To assess safety and effectiveness of BSJ003W, the following three endpoints are established as Co-Primary Endpoints:

1. The occurrence of one of the following events between the time of implant and within 7 days following the procedure or by hospital discharge, whichever is later:

all-cause death, ischemic stroke, systemic embolism, or device- or procedure- related events requiring open cardiac surgery or major endovascular intervention such as pseudoaneurysm repair, AV fistula repair, or other major endovascular repair.

Percutaneous catheter drainage of pericardial effusions, snaring of an embolized device, thrombin injection to treat femoral pseudoaneurysm and nonsurgical treatments of access site complications are excluded from this endpoint.

2. The occurrence of composite events* including stroke (all/ ischemic/ hemorrhagic), systemic embolism and CV death (including unexplained cause) .

*All data collected up to the last patient's 6 months follow-up visit to be completed.

3. The rate of effective LAA closure* at 45 days and 6 months. Change in the rate between the two time points will also be analyzed.

*The effective LAA closure is defined as peri-device flow \leq 5mm demonstrated by TEE. TEE measurements will be assessed by independent Core Lab.

A study to confirm the safety and effectiveness of the BSJ003W in Japanese patients with non-valvular atrial fibrillation at increased risk of thromboembolism in Japanese clinical environment	
Secondary endpoints	
Safety endpoints:
 
 • The occurrence of major bleeding* at 0 – 45 days, 45 days – 6 months, 6 months – 24 months 
*Major bleeding is defined as per BARC bleeding definition type 3 or 5
 
 • Frequency of the following bleeding events at 0 – 45 days, 45 days – 6 months and 6 months – 24 months: • Clinically overt non-fatal bleeding* • All bleeding events 
*Clinically overt non-fatal bleeding is defined as per BARC bleeding definition type 2.
 
Effectiveness endpoints:
 
 • The occurrence of composite events* for effectiveness; stroke (all/ ischemic/ hemorrhagic), systemic embolism and CV death (including unexplained cause) 
*All data collected up to the last patient's 12 months and 24 months follow-up visits to be completed.
 
 • Effective LAA closure at 12-month and its time course until then. • The occurrence of ischemic stroke or systemic embolism (excluding 7 days after implanting or day after hospital discharge whichever is later) at 6 months, 12 months and 24 months.
Additional Endpoints	
Device performance:
 
 • Technical Success defined as successful delivery and release of BSJ003W into the LAA including successful recapture and retrieval if necessary. 
Safety endpoints:
 
 • Occurrence of reportable adverse events • Occurrence of all-cause mortality 
Effectiveness endpoints:
 
 • Individual occurrence of all-cause death, ischemic stroke,

A study to confirm the safety and effectiveness of the BSJ003W in Japanese patients with non-valvular atrial fibrillation at increased risk of thromboembolism in Japanese clinical environment									
	
hemorrhagic stroke, systemic embolization, cardiovascular death (including unexplained cause) at 6-month, 12-month and 24-month.
 
 • Warfarin discontinuation rate at 45 days, 6-month and 12-month • Severity of stroke assessed by NIH Stroke Score, Modified Rankin Scale Score, and Barthel Index 
Other endpoint:
 
 • EQ-5D 								
Required Medication Therapy	
  
 Visit	Medication	
   
 Implant through 45-day visit	ASA+ Warfarin	
 
 45-day visit through 6-month visit	ASA+ Thienopyridine	
 
 Following the 6-month visit	ASA	
  
 
Warfarin therapy should be appropriately monitored and adjusted so as to achieve a therapeutic INR of 2.0- 3.0. For a subject who are 70 years old or older, a therapeutic INR of 2.0 – 2.6 is recommended considering the high risk of major bleeding. Subjects should remain on warfarin until the 45-day TEE evaluation has shown adequate seal of the LAA. If the LAA is not adequately sealed, the subjects should be on warfarin and Aspirin therapy.
	Visit	Medication	Implant through 45-day visit	ASA+ Warfarin	45-day visit through 6-month visit	ASA+ Thienopyridine	Following the 6-month visit	ASA
Visit	Medication								
Implant through 45-day visit	ASA+ Warfarin								
45-day visit through 6-month visit	ASA+ Thienopyridine								
Following the 6-month visit	ASA								
Follow-up Schedule	
Study procedures and follow-up visits will occur as follows:
 
 • Informed consent • Screening • BSJ003W Implant • 45-day Follow-up (45 ± 15 days) • 6-Month Follow-up (180 ± 15 days) • 12-Month Follow-up (365 ± 30 days) • 18-Month Follow-up (540 ± 60 days) • 24-Month Follow-up (730 ± 60 days) 								
Study Duration	
The duration of the study is expected to last approximately 3 years. The duration of individual subject participation is expected to last approximately 2 years.
								

A study to confirm the safety and effectiveness of the BSJ003W in Japanese patients with non-valvular atrial fibrillation at increased risk of thromboembolism in Japanese clinical environment	
Key Inclusion Criteria	
 1. The subject is Japanese, over 20 years old and provides written informed consent to participate in the trial 2. The subject has documented paroxysmal, persistent or permanent non-valvular atrial fibrillation 3. The subject has a calculated CHA₂DS₂-VASc score of 2 or greater and is recommended for long-term oral anti-coagulation therapy 4. The subject is deemed by their physicians to be suitable for anticoagulant therapy and have an appropriate rationale to seek a non-pharmacologic alternative to warfarin 5. The subject is eligible to come off warfarin therapy if the LAA is sealed (i.e. the subject has no other conditions that would require warfarin therapy).
Key Exclusion Criteria	
 1. The subject has a prior stroke (ischemic or hemorrhagic) or TIA within the 90days prior to consent 2. The subject has had a MI either non-ST elevation or ST elevation MI within 90days prior to consent with or without intervention 3. The subject had or is planning to have any cardiac (e.g. cardioversion, coronary angiogram, percutaneous coronary intervention, cardiac ablation, etc.) or non-cardiac invasive or surgical procedure (e.g. cataract surgery, endoscopy, etc.) within 30 days prior or 45 days after the BSJ003W implant 4. The subject has a history of atrial septal repair or has an ASD/PFO device 5. The subject has an implanted mechanical valve prosthesis in any position 6. The subject currently NYHA class IV CHF 7. The subject is contraindicated to aspirin 8. The subject is contraindicated or seriously allergic to thienopyridine 9. The subject is of childbearing potential and is, or plans to become pregnant during the time of the study (method of assessment upon study physician's discretion) 10. The subject is not able and willing to return for required follow-up visits and examinations 11. Subjects who are currently enrolled in another

A study to confirm the safety and effectiveness of the BSJ003W in Japanese patients with non-valvular atrial fibrillation at increased risk of thromboembolism in Japanese clinical environment	
	
investigational study (of which primary endpoint follow-up have not been completed yet).
 
12. The subject has other reason not to be eligible for this study per investigators' discretion.

ECHO Exclusion Criteria	
 1. The subject has LVEF < 30%. 2. The subject has intracardiac thrombus visualized by TEE within 2 days prior to implant. 3. The subject has an existing pericardial effusion with a circumferential echo-free space > 5mm, and/or the patient has signs/symptoms of acute or chronic pericarditis, and/or there is evidence (clinically or echocardiographically) of tamponade physiology. 4. The subject has a high- risk patent foramen ovale (PFO) with an atrial septal aneurysm excursion > 15mm or length \geq 15mm. 5. The subject has a high-risk PFO with a large shunt defined as early, within 3 beats, and/or substantial passage of bubbles. 6. The subject has significant mitral valve stenosis (i.e., MV < 1.5 cm²). 7. The subject has complex atheroma with mobile plaque of the descending aorta and/or aortic arch. 8. The subject has a cardiac tumor.
Multiple Interventions During Index Procedure	No concomitant procedures are to be performed at the time of the BSJ003W implant procedure. This includes, but is not limited to, cardiac ablation procedures, transcatheter valve procedures, cardioversions, pacemaker or ICD generator change, etc.
Statistical Methods	
Statistical consideration and Sample size justification	
The primary safety endpoint (endpoint1) event rate observed in the PREVAIL study was 2.2%. Based on the PREVAIL data only, the exact 95% upper confidence bound for this rate is 4.4%. An additional margin of 5.6% is added to this upper confidence bound to create a performance target of 10.0%. In order to maintain \geq95% probability that the observed estimate from this study is lower than the performance target of 10.0%, 40 subjects are required.
 
The expected primary effectiveness endpoint (endpoint3) rate is 99.3%. Based on this expected rate, and the number of subjects in the PREVAIL study with 6-month TEEs, the corresponding exact 95% lower confidence bound is 97.3%. An additional margin of 3.3% is subtracted from this lower confidence bound to create a

A study to confirm the safety and effectiveness of the BSJ003W in Japanese patients with non-valvular atrial fibrillation at increased risk of thromboembolism in Japanese clinical environment	
	performance target of 94.0%. Accounting for 10% attrition to 6-month TEE follow-up, 40 subjects are required to maintain $\geq 95\%$ probability that the observed estimate from this study is higher than the performance target of 94.0%.
Statistical Test Method	Similarities of this study results will be evaluated with foreign pivotal study results. Roll-in patients' data will be evaluated separately from the data of those patients enrolled after the Roll-in patients and will not be included in the endpoint analysis.

2 INTRODUCTION

This statistical plan addresses the planned analyses for the SALUTE Trial based on the protocol with PDM # 92042733. Specified analyses may be used for scientific presentations and/or manuscripts and may not all be provided to Regulatory Authorities.

3 ENDPOINT ANALYSIS

If and only if the both of primary safety and efficacy endpoints are met Performance Targets (of safety based 10%, of efficacy based 94%), we say that the study objectives are met. So, no overall significant level adjustments are employed. Endpoint 2 is medically observed (no Performance Target).

Roll-in patients' data will be evaluated separately from the data of those patients enrolled after the Roll-in patients and will not be included in the endpoint analysis.

3.1 Primary Safety Endpoint (Endpoint 1)

Primary safety endpoint is the occurrence of one of the following events between the time of implant and within 7 days following the procedure or by hospital discharge, whichever is later:

all-cause death, ischemic stroke, systemic embolism, or device- or procedure-related events requiring open cardiac surgery or major endovascular intervention such as pseudoaneurysm repair, AV fistula repair, or other major endovascular repair.

Percutaneous catheter drainage of pericardial effusions, snaring of an embolized device, thrombin injection to treat femoral pseudoaneurysm and nonsurgical treatments of access site complications are excluded from this endpoint.

Similarities of this study results will be evaluated with foreign pivotal study results.

3.1.1 Hypotheses

Not applicable.

3.1.2 Sample Size

The primary safety endpoint event rate observed in the PREVAIL study was 2.2% and an additional margin was added to create a performance target of less than 10.0%. Considering that 1-2 events may occur by chance, equal or more than 40 subjects will allow at least 3 events or more to occur and with $\geq 95\%$ probability, observed estimate from this study is lower than the performance target.

3.1.3 Statistical Methods

Each event will be evaluated individually and occurrence rate and 95% CI will be calculated.

3.2 Primary Efficacy Endpoints (Endpoint2 and 3)

Followings are primary efficacy endpoints:

Primary efficacy endpoints are the occurrence of composite events including stroke (all/ ischemic/ hemorrhagic), systemic embolism and CV death (including unexplained cause) and the rate of effective LAA closure at 45 days, 6 months and change in rate between the two time points.

TEE measurements will be assessed by independent Core Lab.

3.2.1 Hypotheses

Not applicable.

3.2.2 Sample Size

A performance target of an effective LAA closure rate (endpoint3) of this study, 94.0%, was created by considering an additional margin with 99.3% of the effective LAA closure rate observed in PROTECT AF and PREVAIL studies. Accounting for 10% attrition to 6-month TEE follow-up, 40 subjects are required to maintain $\geq 95\%$ probability that the observed estimate from this study is higher than the performance target of 94.0%. This will allow up to 2 patients whose LAA may not be effectively closed for any reasons at 6 months.

Meantime, sample size of 40 patients were established taken into consideration that 10% of pivotal study sample size was reasonable from standpoint of the study feasibility and similarity comparison of outcomes of this study and the pivotal studies.

3.2.3 Statistical Methods

The occurrence of composite events including stroke (all/ ischemic/ hemorrhagic), systemic embolism and CV death (including unexplained cause) as well as effective LAA closure rate will be calculated and similarities of this study results will be

evaluated with foreign pivotal study results. All data collected up to the last patient's 6 month follow-up completion will be used for the analysis.

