4 GENERAL STATISTICAL METHODS

4.1 Analysis Sets

The analysis set for the Co-Primary Endpoints analysis includes implanted subjects with a completed 6-month visit, i.e. for subjects who withdrawn consent/ missing before 6 month time window will be excluded from the implanted analysis set. The analysis set for the other analyses will be the "intent-to-treat" analysis set, including all implanted or attempted subjects.

Roll-in patients' data will be evaluated separately from the data of those patients enrolled after the Roll-in patients.

Intention-to-Treat (ITT) subjects are included in primary analysis for primary safety and efficacy endpoints as well as secondary endpoints and other endpoints. In addition, Implant subjects alone will be evaluated as needed as reference.

ITT: A subject who signs informed consent and regardless of the study device implanted or not, being enrolled into the study.

IMPLANT and ATTEMPT subjects are included in ITT.

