5 ADDITIONAL DATA ANALYSES

5.1 Other Endpoints/Measurements

Baseline and other results (include other primary and secondary endpoints) will be analyzed descriptively with continuous variables (mean, standard deviation, number of patients, minimum, maximum, etc) and discrete values (frequency table and percentage). Similarities of this study results will be evaluated with foreign pivotal study results if necessary.

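### The co-primary composite (Endpoint 2) has a calendar data cut but no per-subject horizon or time scale, so a percentage at that cut would vary with accrual speed (minor)

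*SAP*

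**What the plan says.** The protocol summary (SAP section 1) defines Endpoint 2 with the footnote "All data collected up to the last patient's 6 months follow-up visit to be completed". Section 3.2.3 repeats the rule: "All data collected up to the last patient's 6 month follow-up completion will be used for the analysis". It adds only that the occurrence of the composite will be calculated and its similarity to the foreign pivotal results evaluated. It names no estimator, time origin, censoring rule or horizon.

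The secondary version of the composite uses the same kind of cut: "All data collected up to the last patient's 12 months and 24 months follow-up visits to be completed".

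Section 5.1 is the only general rule for summarising results. It covers baseline and other results, including other primary and secondary endpoints, and gives "discrete values (frequency table and percentage") for discrete data.

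Fixed time points do appear for related endpoints. The additional endpoints in section 1 list the components individually, among them "hemorrhagic stroke, systemic embolization, cardiovascular death (including unexplained cause) at 6-month, 12-month and 24-month". A secondary endpoint combines ischemic stroke and systemic embolism at the same three times, after an early exclusion window. Neither covers the composite itself.

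Section 3 states that Endpoint 2 has no performance target. Study success rests on Endpoints 1 and 3.

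**The concern.** With staggered entry, a cut at the last subject's 6-month visit gives each subject a different length of follow-up. A percentage of subjects with an event then mixes risks over different periods. It is not a 6-month risk, and it rises with slower enrolment even when the underlying event rate is unchanged.

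This matters because the similarity evaluation is the only use that the SAP states for Endpoint 2. Two percentages from studies with different follow-up cannot be read as similar or dissimilar until both are on one time scale, and the SAP states no scale for either side. The result also belongs to the analysis that section 5.2 designates as primary for submission, so the scale should be fixed before the data are seen.

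**Working it through.** The SAP gives no rate or expected count for Endpoint 2, so there is no figure of its own to reproduce.

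**Inputs**
- Analysable subjects: 40 (section 1).
- Minimum follow-up at the first cut: about 0.5 year (6-month visit of the last subject).
- Accrual period a: not stated. About 3 years of study less about 2 years of participation (section 1) suggests about 1 year. Shown for a = 0.25, 0.5 and 1 year.
- Hazard h: not stated. Assumed constant at 3% per year, with 1% and 5% as a range.
- Accrual assumed uniform, so follow-up T is uniform on (0.5, 0.5 + a).

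**Expected percentage at the cut against the 6-month risk, no drop-out**

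Crude = 1 − [exp(−0.5h) − exp(−(0.5 + a)h)]/(ha). The 6-month risk = 1 − exp(−0.5h), which is 1.49% at h = 0.03.

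| Accrual | Crude at cut | Ratio to 6-month risk | Expected events in 40 |
|---|---|---|---|
| 3 months | 1.86% | 1.25 | 0.74 |
| 6 months | 2.22% | 1.49 | 0.89 |
| 12 months | 2.95% | 1.98 | 1.18 |

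The expected count by a fixed 6 months is 40 × 0.0149 = 0.60. At 12 months of accrual the ratio is 1.99 for h = 1% and 1.97 for h = 5%, so it hardly depends on the assumed hazard.

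**With 10% lost evenly before 6 months**

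The 10% is the SAP's attrition figure for the 6-month TEE, borrowed here as an assumption. Lost subjects stay in the denominator. Their event probability is 1 − [1 − exp(−0.5h)]/(0.5h) = 0.75%, so the crude figure becomes 0.9 × crude + 0.1 × 0.75%. The ratios become 1.17, 1.39 and 1.83.

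**Same count on two scales, without any hazard assumption**

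Patient-years with no drop-out = 40 × (0.5 + a/2) = 25, 30 and 40. One event is always 1/40 = 2.5% (exact 95% CI 0.06% to 13.2%). Per 100 patient-years it is 4.0 (0.1 to 22.3), 3.3 (0.08 to 18.6) or 2.5 (0.06 to 13.9).

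**Secondary composite at the 12-month cut**

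With T uniform on (1, 2) and h = 0.03, the crude figure is 4.40% against a 12-month risk of 2.96%, a ratio of 1.49. At the 24-month cut subjects have reached the end of their planned participation, so the difference is immaterial.

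**The case against.** The strongest reply is that the cut is only a data-inclusion rule. It is compatible with a patient-year rate or a Kaplan-Meier estimate, and the remedy proposed here keeps it. That stands: the gap is the missing scale and horizon, not the cut.

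A reader might infer that the SAP prescribes a crude percentage for Endpoint 2. It does not. Section 3.2.3 leaves the scale open, and the percentage is inferred from section 5.1. It is, however, the only summary on offer. Where the SAP relies on the protocol for a definition it says so (sections 7.3.2 and 7.3.3), and section 3.2.3 contains no such reference.

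The practical effect is also small. At 3% per year and 12 months of accrual, the chance that no subject has a first event between month 6 and the cut is about (1 − 0.0146)^40 = 55%, where 0.0146 = 0.0295 − 0.0149. The crude count then equals the 6-month count. The 1-year accrual is inferred from two approximate durations and may be too long for the 40 analysable subjects, since roll-in subjects come first at each site. The one-event illustration measures no bias, and its intervals overlap almost entirely. With so few events, the 6-month composite could largely be rebuilt from the fixed-time component endpoints, except where one subject has several events. All of this stands and limits the severity, but the co-primary result as specified still has no time base.

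A reader might also tie this to section 4.1, where one sentence says "The analysis set for the Co-Primary Endpoints analysis includes implanted subjects with a completed 6-month visit" and others define wider sets. That conflict affects all co-primary endpoints and is a separate point. It bears on this one only because a subject with an early event might be dropped. The text does not settle this: its explanation of who is excluded names withdrawn consent and missing subjects, not deaths.

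**Conclusion.** The point holds as a minor one. Endpoint 2 has a calendar cut and no stated horizon or scale. If the SAP's only general summary is applied, the percentage averages 1.25 to 1.98 times the 6-month risk for 3 to 12 months of accrual (1.17 to 1.83 with the borrowed 10% attrition). These ratios rest on uniform accrual and a constant 3% hazard. The hazard level matters little, but the accrual period matters a good deal and is not stated.

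The documents do not support a reading that trial success or its error rates are affected. Endpoint 2 has no performance target, no hypothesis is tested on it, and about one event is expected at the assumed hazard. Nor can one say that the comparison with the pivotal studies will be biased in a given direction, because the scale of the pivotal result is not given. What is affected is how a co-primary result is read and whether the similarity evaluation compares like with like.

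**What to change.** In section 3.2.3, keep the data cut and add:

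1. Report the composite as first events per 100 patient-years over all follow-up to the cut, with an exact Poisson 95% CI.
2. Give a Kaplan-Meier estimate at 6 months with a 95% CI. If no event has occurred by then, the usual interval collapses, and the Poisson interval should carry the uncertainty.
3. Measure time from the procedure date (implant or attempt), with censoring at last contact or the data cut.
4. Do the same for the secondary composite at the 12-month cut, with the Kaplan-Meier estimate at 12 months.
5. State the scale and horizon of the pivotal result used, and compare only where they match.
6. For this endpoint, use all non-roll-in subjects who were implanted or attempted, so that nobody with an event before 6 months is left out for lack of a completed 6-month visit. Reconcile the sets in section 4.1 separately.

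Competing-risk estimates and extra work at the 24-month cut are not needed for so few events. The cost is a few sentences in the SAP and minor programming, with no new data. The intervals will be wide.
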